1.0 Abstract

Introduction

Transcutaneous Electrical Nerve Stimulation (TENS) therapy has been used for the control of postoperative pain with variable results.[1-9] TENS therapy is also considered an appropriate non-pharmacologic adjunct to patient care in the setting of symptomatic knee arthritis.[10-28] Recently, orthopaedic surgeons have begun to utilize TENS therapy about the operative site in the early post-operative period because of several proposed benefits including pain relief with decreased analgesic requirements, increased quadriceps strength with decreased postoperative muscle atrophy. To our knowledge, the use of TENS as an adjunct to post-operative analgesia in the setting of outpatient knee arthroscopy has not been extensively studied. We propose a pilot study to determine the effectiveness of TENS therapy in the early post-operative period following knee arthroscopy for meniscectomy, synovectomy, or chondroplasty.

Methods

Consecutive patients meeting inclusion criteria will be randomized to one of two treatment groups: 1) structured TENS therapy (n=10) or 2) sham TENS therapy (n=10). Patients and the surgeon will be blinded to the TENS treatment group. Patients will complete preoperative assessments of pain and function using standardized outcomes instruments, then complete daily pain assessments and reports of analgesic consumption in the early post-operative period (two weeks). TENS will be discontinued at two weeks post-operatively. The surgeon will complete the IKDC Surgical Document Form with information from the surgical procedure. Patients will be followed for a total of six months post-operatively with clinical measurements of quadriceps strength, knee range of motion, presence of effusion, and quadriceps circumference (measure of atrophy). Functional outcomes will be measured with KOOS, Marx, Lysholm, IKDC, and SF-12 for up to six

months post-operatively. Statistical analysis will be performed using computer software and significance defined as $p < 0.05$.

The results of the pilot study will be used to design a multi-center prospective randomized clinical trial.

Conclusion

TENS therapy in the early post-operative period following outpatient knee arthroscopy has not been extensively studied. This pilot study will provide initial information for the effectiveness of this widely-used clinical device.

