2.0 Specific Aims

Transcutaneous Electrical Nerve Stimulation (TENS) therapy has been used for control of knee pain with good results. Documented benefits of non-pharmacologic post-surgical pain control using TENS include decreased opioid analgesic usage, increased muscle strength, with a relative lack of side-effects.[1-9] Additionally, TENS therapy has been studied extensively for the nonoperative treatment of knee arthritic conditions with somewhat mixed results.

Knee arthroscopy in the outpatient setting often requires a patient's pain to be well controlled in order to ensure day of surgery discharge. In the early post-operative period, pain is primarily controlled with a combination of modalities including cryotherapy, narcotic and non-steroidal analgesia. To our knowledge, the use of TENS as an adjunct to post-operative analgesia in the setting of outpatient knee arthroscopy has not been studied extensively. To this end, we propose the following hypothesis:

Hypothesis: Following standard of care procedures for arthroscopy knee surgery it is anticipated that Transcutaneous Electrical Nerve Stimulation (TENS) will provide improved pain relieve and improve functional outcomes.

Specific Aim 1: Determine patient's perception of pain in the early post-operative period while utilizing structure TENS therapy.

Specific Aim 2: Determine the short-term (6 months) outcomes following knee arthroscopy while using TENS in the early post-operative period.

Specific Aim 3: Determine effect of early TENS use on quadriceps strength and tone in the early and intermediate post-operative periods.

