9.0 Proposed Timeline

- Pre-study: Patient questionnaire and database constructed.
- 0-3 months: Patient enrollment begins.
- 3-9 months: Data collection. Initial data analysis of immediate post-operative pain logs.
- 9-12 months: Data analysis.
- 12-14 months: Pilot study completion and preparation for multi-center study. Power analysis will be performed to determine the number of patients needed to enroll.

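### With p < 0.05 as the only analysis rule, and no primary outcome, primary time point or multiplicity rule, a chance finding on any outcome or visit could be reported as evidence that TENS works

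*Combined protocol and SAP*

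**What the plan says.** The whole statistical method is one sentence in section 1.0 (Methods): "Statistical analysis will be performed using computer software and significance defined as" p < 0.05. It names no outcome, time point, test or model, and does not say whether tests are one- or two-sided.

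The purpose is stated in two ways. The Introduction says "We propose a pilot study to determine the effectiveness of TENS therapy in the early post-operative period". The Conclusion is more modest: "This pilot study will provide initial information for the effectiveness of this widely-used clinical device".

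Section 2.0 gives one hypothesis covering two domains, that TENS "will provide improved pain relieve and improve functional outcomes". Three aims follow, unranked:

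- Aim 1 concerns "perception of pain in the early post-operative period while utilizing structure TENS therapy", with no summary measure or day.
- Aim 2 is "Determine the short-term (6 months) outcomes following knee arthroscopy while using TENS in the early post-operative period", with no instrument.
- Aim 3 is "Determine effect of early TENS use on quadriceps strength and tone in the early and intermediate post-operative periods".

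Appendix E schedules 11 outcomes: pain, medication use, range of motion, effusion, strength, thigh circumference, KOOS, Marx, Lysholm, IKDC and SF-12. The four clinical measures are taken at five post-operative visits. The questionnaires, pain VAS and medication use are taken at three (6 weeks, 12 weeks, 6 months). The Appendix D diary covers days 1-14. Section 9.0 places "Initial data analysis of immediate post-operative pain logs" in the data-collection period, with no rule attached, and a power analysis for the multi-center trial at the end.

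**The concern.** A significance threshold controls the false-positive rate only when it is clear which comparison it applies to. Here it is attached to none, so it could be applied to any of them. A report that one questionnaire at one visit, or one way of averaging the diary, reached p < 0.05 would comply with the plan as written. So would a choice of headline outcome made after the first look at the pain logs.

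Even diary pain is not one fixed outcome. Each day has 8 rating times: 3 at treatment times, 3 half an hour later and 2 others. No section says which ratings count.

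At stake is how far a p-value from this pilot can be believed when it is cited as evidence about the device. With 10 patients per arm, an outcome singled out because it crossed the threshold will also tend to show an exaggerated effect, and that estimate could feed the power analysis for the next trial.

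**Working it through.** The plan states no error rate to reproduce, and 10 per group is given without an effect size, SD or power. The check therefore asks how the chance of a false result favouring TENS depends on how the p < 0.05 rule is used.

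**Inputs from the documents.** Threshold 0.05 (section 1.0); 10 per arm (section 7.0); three aims (section 2.0); outcomes and visits (Appendix E); diary times (Appendix D).

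**Assumptions.** Inert device; two-sided pooled t-tests (18 degrees of freedom), so 2.5% per test in favour of TENS; normal data; any p < 0.05 favouring TENS counts. Correlations are assumed.

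**Counts.**
- One test per aim: 3.
- One test per outcome: 11.
- Each outcome at each visit: pain 4 (diary summary + 3 VAS) + medication 4 (diary summary + 3) + clinical 4 × 5 = 20 + questionnaires 5 × 3 = 15, in total 43.
- Diary ratings per patient, days 1-14: 8 × 14 = 112 = 42 pre-treatment + 42 post-treatment + 28 other.

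**Independent tests.** Chance = 1 − 0.975^m.
- m = 3: 1 − 0.975^3 = 0.073
- m = 11: 1 − 0.975^11 = 0.243
- m = 43: 1 − 0.975^43 = 0.663

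**Correlated tests**, simulated with 10 per arm:

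| Tests | Correlation | False result favouring TENS |
|---|---|---|
| 1 | – | 2.5% |
| 3 | 0.5 | 6.3% |
| 3 | 0.9 | 4.2% |
| 11 | 0.5 | 15.7% |
| 11 | 0.9 | 6.8% |
| 43 | 0.7 within / 0.3 between outcomes | 38% |
| 43 | 0.8 / 0.5 | 28% |
| 43 | 0.9 / 0.7 | 18% |

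**Cross-check.** For m equicorrelated normal tests, the chance is 1 − ∫ φ(u) Φ[(1.96 − √ρ u)/√(1 − ρ)]^m du. This gives 6.3% and 4.2% for 3 tests (ρ = 0.5, 0.9) and 15.2% and 6.6% for 11. For 43 tests with one common correlation it gives 42% at 0.3, 30% at 0.5 and 14% at 0.8, so the 43-test result depends heavily on the assumed structure.

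**Other readings.**
- One-sided tests at 0.05: 5% for one test, 8-14% for 3, 12-43% for 11, and 29-56% for 43 in the three correlated cases.
- Pain and at least one questionnaire both significant in favour of TENS: 0.3% (correlation 0) to 2.1% (0.9) with 11 tests; 3.3-3.5% with 43 tests.
- Diary pain alone, with the readings (all, pre or post) and baseline adjustment left open: 4.4-6.3%, against about 2.5% for one fixed version.

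**Precision.** The 95% CI half-width for a difference in means is 2.101 × √(2/10) = 0.94 SD. Unadjusted power at two-sided 0.05 is 18.5% for 0.5 SD and 39.5% for 0.8 SD; 80% power needs about 1.32 SD.

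**The case against.** The strongest reply is that the plan never says any p < 0.05 counts. The hypothesis joins pain and function. If both must be shown and pain is a single test, the chance cannot exceed the 2.5% of the pain test, and the 11-test figures (0.3-2.1%) are below it. This stands: on the joint reading there is little or no inflation. It does not close the gap, because the plan neither states that reading nor excludes a claim on one outcome.

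Second, no section plans 43 tests. Section 5.2 includes the Lysholm scale for comparison with earlier work, and no aim mentions range of motion or effusion. Without these, 43 − 3 − 10 = 30 tests remain. The aims and timeline also point towards early pain. This stands as a limit on the 43-test scenario, the one with least support in the text. The direction is unchanged: even 20 tests at a common correlation of 0.5 give 21%. Normality is also only approximate for effusion grades, pill counts and 0-10 ratings.

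Third, this is a 20-patient pilot. No section ties p < 0.05 to a go/no-go decision, and choosing the next trial's outcome from pilot data is a normal use of a pilot, since the new trial tests it on new patients. This stands and lowers the severity. What remains is that the plan sets a significance threshold and speaks of determining effectiveness.

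**Conclusion.** The gap is real and should be fixed. The plan gives a significance threshold without saying what it applies to, so a single chance result on any of 11 outcomes could be reported as evidence of effectiveness. If any p < 0.05 counts, the chance of a false result favouring TENS exceeds the single-test 2.5% in every scenario examined: about 4-7% with one test per aim, 7-24% with one per outcome and 18-38% with 43 tests in the three structured cases. These figures rest on two-sided t-tests, an inert device and assumed correlations, and they are not bounds.

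A reader might infer that the trial has a 38% or even a 66% false-positive rate. The documents do not support that. The first needs a test count and correlations they do not give. The second needs independent tests, which is not credible for repeated measures on the same 20 patients. Nor do the documents support the inference that the pilot is unfit to inform a later trial. The defect is in what could be claimed from its p-values.

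**What to change.** Before the initial pain-log analysis and before unblinding, adopt one of two options.

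(a) If a significance claim is wanted, name one primary TENS-versus-sham comparison that fits Aim 1 and uses data already collected, for example diary pain over days 1-14. State which readings count (for example all 112, or only the 42 pre-treatment ones). Specify one model only, for example a mixed model of daily means adjusted for the pre-operative pain VAS, with all randomised patients in their assigned group. Patients with some missing days then stay in the analysis. Test it once at two-sided 0.05. Report every other outcome and time point as a between-group estimate with a 95% CI, labelled exploratory, with no significance claim. The sponsor may prefer another single outcome and time point.

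(b) If no effectiveness claim is wanted from the pilot, remove the p < 0.05 rule and report estimates with 95% CIs only.

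Under either option, state that with 10 per arm a non-significant or imprecise result does not show absence of effect.

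The cost is a few sentences of text and no new data. Secondary outcomes can no longer be called significant, and under (a) the single test detects only large effects.

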2.0 Specific Aims

Transcutaneous Electrical Nerve Stimulation (TENS) therapy has been used for control of knee pain with good results. Documented benefits of non-pharmacologic post-surgical pain control using TENS include decreased opioid analgesic usage, increased muscle strength, with a relative lack of side-effects.[1-9] Additionally, TENS therapy has been studied extensively for the nonoperative treatment of knee arthritic conditions with somewhat mixed results.

Knee arthroscopy in the outpatient setting often requires a patient's pain to be well controlled in order to ensure day of surgery discharge. In the early post-operative period, pain is primarily controlled with a combination of modalities including cryotherapy, narcotic and non-steroidal analgesia. To our knowledge, the use of TENS as an adjunct to post-operative analgesia in the setting of outpatient knee arthroscopy has not been studied extensively. To this end, we propose the following hypothesis:

Hypothesis: Following standard of care procedures for arthroscopy knee surgery it is anticipated that Transcutaneous Electrical Nerve Stimulation (TENS) will provide improved pain relieve and improve functional outcomes.

Specific Aim 1: Determine patient's perception of pain in the early post-operative period while utilizing structure TENS therapy.

Specific Aim 2: Determine the short-term (6 months) outcomes following knee arthroscopy while using TENS in the early post-operative period.

Specific Aim 3: Determine effect of early TENS use on quadriceps strength and tone in the early and intermediate post-operative periods.

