7.0 Randomization Procedure

Patients will be randomized using a block randomization scheme generated by the statistician. Sealed envelopes will be used to conceal the random assignments of patients to one of two treatment groups in the immediate post-operative period.

- Group 1: structured TENS therapy (n=10)
- Group 2: sham TENS therapy (n=10)

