8.0 Patient Form (Week 1 and 2 post-operative)

Patients will complete a pain and analgesic usage diary. Additionally, patients will complete VAS pain questions daily and pre- and post-TENS treatment. See Appendix D. TENS treatment will be standardized and will consist of 20 minute sessions three times per day at the manufacturer's recommended settings.

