Appendix B. Physician-entered Data at each evaluation

Participant ID # _____

Time	ROM (R/L)	Effusion (R/L)	Strength (R/L)	Quad Circ (R/L)	Other
Pre-op					
1 week					
2 weeks					
6 weeks					
12 weeks					

6 months					
-----------------	--	--	--	--	--

- ROM ("3-0-135")
- Effusion (none, 1+, 2+, 3+)
- Strength (lbs) using hand-held dynamometer
- Thigh circumference (cm) measured 10 cm proximal to superior pole of the patella Other comments

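### No form or schedule shown prompts for adverse events or device tolerability, so the pilot has no systematic record by arm of skin reactions, device problems or intolerance

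*Combined protocol and SAP*

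**What the plan says.** Section 2.0 (Specific Aims) lists a "relative lack of side-effects" among the documented benefits of TENS for post-surgical pain control, citing earlier studies. The hypothesis and the three aims concern pain, functional outcomes, and quadriceps strength and tone; none concerns safety.

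Section 8.0 sets device use at "20 minute sessions three times per day", and the Appendix D diary lays this out for Days 1 to 14. Section 7.0 allocates 10 patients to TENS and 10 to sham. The Abstract says "Patients will be followed for a total of six months post-operatively" and that the results will be used to design a multi-center trial. For that next trial, section 9.0 names one specific analysis, a power calculation.

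The data collection shown is as follows:

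- **Appendix B** ("Physician-entered Data at each evaluation"): range of motion, effusion, strength, thigh circumference, and an Other column without a prompt.
- **Appendix C** (pre-operative): current pain medication and current pain.
- **Appendix D** (diary): pain score, number of pain pills, the treatment to be done, and a completion mark.
- **Appendix E** (schedule): questionnaires, pain VAS, medication use, surgical data, and the four Appendix B measurements.

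**The concern.** The plan cites tolerability as an advantage of the device but includes no question that would record it. A patient with irritated skin under an electrode, a faulty unit, or stimulation too unpleasant to continue has no place to say so. An empty completion box looks the same whether the patient forgot the session, the device failed, or the patient stopped because of discomfort. For the larger trial those three explanations mean different things.

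The timing makes this more than a missing detail. An analysis choice can still be settled after the data are in, but an event nobody asked about generally cannot be reconstructed, least of all in the same way for both arms. The pilot would then reach the multi-center design stage with no count of patients with device-related events and no denominator for one.

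**Working it through.** The plan states no safety figure, so there is none to reproduce. The check is of the forms first, then of what a prompted item could deliver.

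**1. Does any form shown ask?** Going through Appendices B, C, D and E field by field, none has an item on adverse events, skin reactions, device problems, or stopping because of the device. Appendices F and G are named but not reproduced. F is a surgical form that Appendix E places intraoperatively, before the first diary treatment on Day 1. G holds the outcome instruments, which section 5.2 describes as covering symptoms, function, activity and quality of life.

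**2. Could existing items stand in?**

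- Effusion, range of motion and strength describe recovery of the knee. They do not register a skin or device problem.
- Pain scores around sessions could show pain rising after treatment, but not why.
- KOOS covers symptoms and Lysholm covers swelling. Appendix E names them pre-operatively and then at 6 weeks, 12 weeks and 6 months. The 1- and 2-week rows refer back to the entries above, which I read as pain and medication use. The first post-operative questionnaire is then 6 − 2 = 4 weeks after TENS stops.
- The Other column in Appendix B can hold a note. It has no prompt, so a blank cannot be read as no event.

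**3. Exposure without a prompted question.** 3 sessions per day × 14 days = 42 scheduled sessions per patient. In the active arm that is 10 × 42 = 420, if every session is done. The diary has 14 × 8 + 2 = 114 entry rows per patient and no event field.

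**4. What a prompted item would give with 10 per arm.** The documents give no event rate, so the rates below are assumptions. The chance of at least one patient with an event is 1 − (1 − p)^10:

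| Assumed true rate p | Calculation | Chance of at least one in 10 |
|---|---|---|
| 1% | 1 − 0.99^10 | 9.6% |
| 5% | 1 − 0.95^10 | 40.1% |
| 10% | 1 − 0.90^10 | 65.1% |
| 20% | 1 − 0.80^10 | 89.3% |

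Exact upper limits if 0 of 10 have an event:

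- two-sided 95%: 1 − 0.025^(1/10) = 30.8%
- one-sided 95%: 1 − 0.05^(1/10) = 25.9%

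For 1 of 10, the exact two-sided 95% limits are 0.3% and 44.5%.

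**5. Could the arms be compared by a test?** Hardly. By Fisher's exact test (two-sided), 4/10 against 0/10 gives p = 0.087 and 5/10 against 0/10 gives p = 0.033. Against an arm with no events, at least half the patients in the other arm would need one.

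**The case against.** The strongest case on the other side has four parts.

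*Harm-related data are already collected.* Effusion, range of motion, pain before and after sessions, pill counts and session completion are recorded in both arms and can be tabulated. This stands. A reader might infer that the pilot cannot report any harm by arm, or that every event would go unrecorded. The documents do not support that: these measures exist, and a physician can write an event in the Other column. What is missing is prompted, comparable capture of device and skin problems.

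*Safety is not an objective.* This also stands in part. A reader might infer that the trial's rationale depends on tolerability. In the text it is one cited benefit among several, absent from the aims and hypothesis, and the only analysis named for the next trial is a power calculation. But a trial of a device does not need a safety aim for a basic tolerability question to be worthwhile.

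*Reporting rules may sit elsewhere.* Title and consent pages are not in the text reviewed, so a general event-reporting procedure cannot be excluded. It would be wrong to conclude that the trial has none. Such a rule would still not put a standard question on the forms shown.

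*Ten per arm is too few.* It is too few for a comparison or for ruling out uncommon events. It is enough for a description: a count with wide limits can be reported, whereas an unprompted field supports no count at all.

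One caution concerns the remedy. The surgeon is to be blinded and Appendix B is physician-entered, so a question there about skin under the electrodes could hint at allocation. A single item mixing device problems with all other events would also let ordinary surgical complaints obscure the device signal.

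**Conclusion.** The point holds in a limited form. No form or schedule shown prompts for adverse events or device tolerability, and the items that are collected do not replace such a prompt over 42 scheduled sessions per patient. The loss is permanent once patients have passed through the two treatment weeks.

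The gain from asking is real but modest: counts by arm, with zero of 10 still compatible with a true rate of up to 30.8% (two-sided 95%). At an assumed rate of 1%, an arm of 10 would show no event about nine times in ten. The item would therefore help to find common tolerability problems and would say little about rare ones.

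This rests on three assumptions: that Appendices F and G contain what their titles and section 5.2 indicate; that the true event rate is unknown, with 1% to 20% used only as illustration; and that sham patients also wear electrodes, so that one wording fits both arms.

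**What to change.** Before enrolment, add two separate yes/no items for the patient to complete at the end of each diary week, after the Day 7 and Day 14 blocks of Appendix D, worded identically in both arms:

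- (a) *Have you had any problem with the device or with the skin under the electrodes?*
- (b) *Have you had any other adverse event?*

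Each is followed by date and description. Patient completion means that the blinded surgeon need not ask about the electrodes. Separating (a) from (b) keeps surgical complaints out of the device count.

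List both items in Appendix E at 1 and 2 weeks. State in the analysis plan that the number of patients with any event, counted once per patient and separately for (a) and (b), will be reported by arm with exact two-sided 95% limits and the number who answered, descriptively and without a between-arm test.

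The cost is two short patient entries in each of two weeks and one table. Sample size, visits and treatment do not change. The downside is low precision, which the report should state so that an absence of events is not read as evidence of safety.
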